1.2 RATIONALE FOR CURRENT STUDY

Research question: Can kisspeptin stimulate oocyte maturation in IVF therapy for infertility ?

Hypothesis: kisspeptin will stimulate oocyte maturation in IVF therapy for infertility

Infertility affects one in six couples in the UK (1). IVF treatment is now widely and successfully used to enable infertile couples to conceive. Approximately 45,000 cycles of IVF are performed in Britain each year. However, IVF treatment can result in the potentially life threatening condition, OHSS (2). Mild forms of OHSS occur in approximately 1 in 3 of all IVF cycles, whilst approximately 1 in 10 IVF cycles result in moderate or severe OHSS (3). The major cause of OHSS is the pharmacological use of hCG to stimulate oocyte maturation in current IVF protocols (4). The development of a more physiological stimulus for oocyte maturation should avoid this dangerous side effect and improve the safety and efficacy of IVF treatment (5). Kisspeptin is a hormone which stimulates reproductive hormone secretion in animals and is responsible for the endogenous LH surge which results in ovulation (6). In keeping

with this, exogenous administration of kisspeptin has been shown to induce ovulation in rats and sheep (31, 32). We have conducted the first studies of kisspeptin administration to humans; in which we have shown that acute administration of kisspeptin potently stimulates reproductive hormone secretion in healthy men and women (7, 8), as well as women with infertility due to hypothalamic amenorrhea (33). Importantly, we have demonstrated that healthy women with regular menstrual cycles are most sensitive to the effects of kisspeptin immediately prior to ovulation (8). Recent evidence demonstrates that kisspeptin stimulates the release of a limited pool of endogenous GnRH which results in the release of endogenous gonadotrophins (9-11). Therefore, the significant advantage of kisspeptin over current treatments is that its effects would depend on the sensitivity of an individual's HPG axis. This would result in a more physiological LH surge and oocyte maturation during IVF treatment, thereby improving safety and efficacy of IVF treatment (5).

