6. TREATMENTS

6.1 TREATMENT ARMS

All of the women in this study will undergo a standard FSH/GnRH antagonist IVF protocol with luteal phase supplementation which is used for women undergoing IVF treatment at Hammersmith Hospital under the supervision of [name] (Director of the IVF Unit) (please see appendix 2). The only difference will be that women taking part in the study will have either one or two subcutaneous injections of kisspeptin in place of hCG in order to trigger oocyte maturation. This injection will be administered by two experienced physicians at the Hammersmith Hospital or in the participant's home according to the patients preference.

The patients will be administered with the first dose of kisspeptin 12-24 hours after the last injection of FSH/GnRH antagonist for final oocyte maturation. Women will be randomised to receive either a single dose of kisspeptin (9.6nmol/kg), or two doses of kisspeptin 8-12 hours apart. The optimal dosing regimen of kisspeptin will be the dose of kisspeptin which causes the highest level of oocyte maturation.

Since kisspeptin causes a rapid and potent rise in LH release following sc injection we would expect that kisspeptin will induce oocyte maturation at a similar timing as when hCG or GnRH are used to trigger oocyte maturation which is 32-36 hours after injection (13, 16, 17, 18). In order to determine the changes in reproductive hormones which occur during oocyte maturation, participants will be given two options for blood testing following injection of kisspeptin. These options will be discussed at screening, and participants are entirely free to decline overnight blood sampling without altering their study participation or clinical care:

Option 1. Overnight blood sampling: Participants opting for overnight blood sampling will be admitted to the Wellcome / NIHR Clinical Research Facility (CRF), Hammersmith Hospital. Blood will be sampled for measurement of plasma LH, FSH, progesterone, kisspeptin and oestradiol. Total blood loss will not exceed 100ml, and blood sampling will not be performed more frequently than every 15min.

Option 2. Less intensive blood testing: In participants who do not opt into overnight blood sampling, plasma LH, FSH, progesterone and oestradiol will be measured immediately before kisspeptin injection, on up to six occasions within the first 24h following kisspeptin injection (according to participant availability), and then at the time of oocyte retrieval.

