**The use of the Hormone Kisspeptin in *in vitro* fertilisation (IVF) treatment.
Statistical Analysis Plan, version 3.0**

Date: 24/06/2015

MAIN SPONSOR: Imperial College London

FUNDERS: Medical Research Council (MRC)

STUDY COORDINATION CENTRE: Imperial College London

Protocol Code Number ICL/KISS/12/01

EudraCT number 2012-000154-61

Research Ethics Committee (REC) reference: 10/H0707/2

NCT No. NCT01667406

Statistical Analysis Plan, version 3.0

Date: 24/06/2015

Study: One versus 2 doses of kisspeptin (10hrs apart)

Participants will undergo controlled ovarian stimulation using a recombinant FSH/GnRH antagonist protocol and receive either one (Single) or two doses (Double) of kisspeptin-54 (9.6nmol/kg each dose) to trigger oocyte maturation.

On day 2 or 3 of the menstrual cycle, patients will receive daily SC recombinant FSH (recFSH) injections (Gonal F 112.5 IU, Merck Serono, Geneva, Switzerland, administered daily at midday); pelvic ultrasound scan will be performed five days after commencing recFSH, to determine ovarian follicular development. Daily subcutaneous GnRH antagonist injections (Cetrotide 0.25mg, Merck Serono, injected at 9pm daily) will be used to inhibit a premature LH surge, and will be commenced on day 5 of recombinant FSH injections. If serum LH is undetectable (<0.5 IU/L) on Day 7 of recombinant FSH injections, then the dose of cetrotide will be halved to 0.125mg daily. Further ultrasound scans will be performed according to follicular size and response to superovulation. When at least three ovarian follicles \geq 18mm diameter are visible on ultrasound, all patients will receive a subcutaneous bolus injection of kisspeptin-54 administered by a study investigator to trigger oocyte maturation at 36hrs prior to egg collection (between 2030 and 2300h). The dose of kisspeptin-54 will be weight-adjusted (9.6nmol/kg). Patients will then be randomized to receive either a second dose of kisspeptin (9.6nmol/kg), or saline placebo injection at 10hrs following the first kisspeptin trigger injection.

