The final dose of GnRH antagonist will be administered 24 hours prior to kisspeptin-54. Serum LH, FSH, oestradiol and progesterone will be measured immediately before, 12hrs and 36hrs after kisspeptin-54 injection, and at the time of egg retrieval in all women. Transvaginal ultrasound-directed oocyte retrieval (TVOR) will be carried out 36h following kisspeptin administration under intravenous anaesthesia (propofol). Intracytoplasmic sperm injection (ICSI) will be performed in all study cycles using sperm from the male partner to allow for assessment of oocyte maturation. All embryos will be graded at day 3 by an independent embryologist, blinded to doses of kisspeptin administered, using the British Fertility Society (BFS) and Association of Clinical Embryologist (ACE) embryo grading scheme for cleavage stage embryos, which describes embryos based on cell number, blastomere size and fragmentation.(30) If at day 3 at least 2 embryos have 6 or more cells, <20% difference in blastomere diameter and <50% fragmentation, they will be incubated until day 5 post oocyte retrieval in order that the strongest embryos can be identified for transfer. At Day 5, embryos will be graded for blastocyst expansion (1 to 6), inner cell mass (A to E) and trophectoderm (A to C).(30) At blastocyst stage, embryos which score at least 3 for blastocyst expansion and A or B for inner cell mass and trophectoderm will be classified as 'high quality embryos'. One or two embryos of highest quality during morphological assessment will be transferred to the uterine cavity 3-5 days following oocyte retrieval.

Assessment of Ovarian Hyperstimulation Syndrome (OHSS)

All women recruited to the study will be regarded as being at high risk of OHSS. Therefore women will be routinely screened for the development of early OHSS (assessed at embryo transfer 3-5days following oocyte retrieval) and late OHSS (assessed 11days following embryo transfer). Women will be screened by symptoms (abdominal pain, abdominal bloating, diarrhoea, nausea, vomiting, subjective reduction in urine output), blood analysis (hemoglobin, hematocrit, white cell count, liver function, renal function, coagulation profile) and ultrasound parameters (ovarian size, presence of free

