fluid in pouch of douglas, adnexae, abdomen or pleural cavity). OHSS will be graded according to the criteria of Golan et al. 1989 with updated categorization by Navot et al. 1992.(16,17) OHSS will be independently graded by two experienced IVF clinicians external to the study team ([name] and [name]), who will be provided with blinded data concerning patient symptom, blood analysis and ultrasound parameters. In the event of any discrepancy in categorization of OHSS, the more severe classification will be used.

Study outcomes

The primary outcome is proportion of patients achieving optimal oocyte yield (percentage of mature (metaphase 2; M2) oocytes collected from the number of follicles ≥ 14 mm in size on final ultrasound scan prior to kisspeptin-54 trigger administration of at least 60%). All women will have an ultrasound on the morning of kisspeptin trigger administration. Oocytes will be independently classified as M2 by presence of the first polar body and round ooplasm, by an embryologist blinded to whether one or 2 doses of kisspeptin-54 were administered.

Secondary outcomes are the occurrence of OHSS, fertilization rate (percentage of M2 oocytes which fertilize to form two pronuclear (2PN) zygotes following intracytoplasmic injection with sperm; ICSI), embryo formation and quality, biochemical pregnancy rate (serum β hCG > 10 mIU/mL eleven days after embryo transfer) and clinical pregnancy rate (intrauterine gestational sac with heartbeat on ultrasound at six weeks gestation).

Primary Outcome:

Proportion of patients achieving optimal oocyte yield (defined as proportion of mature eggs collected from follicles of at least 14mm in size on final ultrasound prior to egg collection being at least 60%) (Binary Outcome).

The main covariates to be considered are the number of follicles on final ultrasound scan prior to trigger (follicles ≥ 14 mm on day of trigger), serum AMH, Antral Follicle Count, age, pretrigger estradiol level.

Absolute difference between two groups with CIs will be calculated.

Secondary outcomes:

-Change in reproductive hormones LH, FSH, Estradiol and progesterone from pretrigger values to 4hr, 10hr, 14hr and 20hr values.

Variables to be included in the model: weight, AMH, pretrigger reproductive hormone levels.

Pregnancy (binary) and Implantation rates (ordinal- can be 0, 50 or 100%)-

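### The SAP hormone models omit the level just before the second injection as a covariate, which costs precision but not validity in the 14 h and 20 h comparisons

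*SAP*

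**What the plan says.** In the SAP's study description, "all patients will receive a subcutaneous bolus injection of kisspeptin-54". Women are then randomised to a second kisspeptin injection or a "saline placebo injection at 10hrs following the first kisspeptin trigger injection". Until that second injection the two arms are treated identically.

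Under Secondary outcomes, the hormone endpoint is "Change in reproductive hormones LH, FSH, Estradiol and progesterone from pretrigger values to 4hr, 10hr, 14hr and 20hr values", followed by "Variables to be included in the model: weight, AMH, pretrigger reproductive hormone levels". No value after the first injection is listed as a covariate; the 10 h value appears only as an outcome.

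Two other places bear on whether a 10 h value can serve as a covariate:

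- The SAP's sampling text says "Serum LH, FSH, oestradiol and progesterone will be measured immediately before, 12hrs and 36hrs after kisspeptin-54 injection", and again at egg retrieval. It names no 4, 10, 14 or 20 h sample.
- Protocol section 6.1 describes "two doses of kisspeptin 8-12 hours apart", where the SAP fixes 10 h. The same section's less intensive sampling option allows up to six samples in the first 24 h, depending on when the woman can attend.

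Neither document says whether the 10 h sample is drawn before or after the second injection.

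**The concern.** The randomised question is what a second injection adds. Its natural baseline is the hormone level just before that injection, because this level already reflects how each woman responded to the first dose. The protocol itself expects women to differ here: section 1.2 says of kisspeptin that "its effects would depend on the sensitivity of an individual's HPG axis". A pretrigger value cannot show that response. A sample taken before the second injection may show it, and allocation cannot affect it, so it is a legitimate covariate.

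Without it, the between-woman spread in first-dose response stays in the residual variance of the 14 h and 20 h comparisons. With 31 women per arm, that could widen the intervals noticeably. In addition, the 4 h values, and the 10 h values if drawn pre-dose, precede any difference in treatment. Between-arm tests at those times would be comparisons that are null by design.

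**Working it through.** **Figures in the documents.** Neither document gives a power or precision calculation for the hormone comparison or for the 31 per group. The only LH calculation (protocol section 9: 13 per dose for at least 90% power at 148 IU/L, SD 78 IU/L) belongs to the dose-escalation design. A two-sided 5% t-test for 148 IU/L needs 7 per group at 90% power, and 13 per group gives 99.6%. Thirteen is what the 106 IU/L in the same paragraph needs (power 91.4%). That mismatch does not bear on this point; only the SD is borrowed below.

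**Inputs.**
- n = 31 per arm (SAP).
- SD 78 IU/L for LH (protocol section 9; normal preovulatory women at 12.8 nmol/kg, so only a rough guide here). Percentage gains do not depend on it.
- Correlations, all assumed: r0 (pretrigger with later value), r10 (10 h with later value) and ρ (pretrigger with 10 h), with ρ set equal to r0.

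**Formulas.** With the pretrigger value as covariate, modelling change or the later value gives the same treatment coefficient.
- SAP model: R²a = r0².
- With the 10 h value: R²b = (r0² + r10² − 2·r0·r10·ρ) / (1 − ρ²).
- Variance ratio = (1 − R²b)/(1 − R²a); SE ratio is its square root; equivalent patient multiple is its reciprocal.

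**Worked case, r0 = ρ = 0.3.**
- r10 = 0.5: R²b = (0.09 + 0.25 − 0.09)/0.91 = 0.275. Variance ratio 0.725/0.91 = 0.80; SE ratio 0.89 (11% cut); multiple 1.25.
- r10 = 0.7: R²b = (0.09 + 0.49 − 0.126)/0.91 = 0.499. Variance ratio 0.501/0.91 = 0.55; SE ratio 0.74 (26% cut); multiple 1.82.

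**Range.**

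| r0 = ρ | r10 | R²a | R²b | SE ratio | Patient multiple |
|---|---|---|---|---|---|
| 0.3 | 0.3 | 0.09 | 0.14 | 0.97 | 1.06 |
| 0.3 | 0.5 | 0.09 | 0.27 | 0.89 | 1.25 |
| 0.3 | 0.7 | 0.09 | 0.50 | 0.74 | 1.82 |
| 0.5 | 0.2 or 0.3 | 0.25 | 0.25 | 1.00 | 1.00 |
| 0.5 | 0.5 | 0.25 | 0.33 | 0.94 | 1.13 |
| 0.5 | 0.7 | 0.25 | 0.52 | 0.80 | 1.56 |

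**On the LH scale, r0 = 0.3.** SE = 78·√(1 − R²)·√(2/31). It is 18.9 IU/L for the SAP model, 16.9 with r10 = 0.5 and 14.0 with r10 = 0.7. The difference detectable with 80% power is 53.9, 48.1 and 40.0 IU/L respectively. Residual degrees of freedom fall from 57 to 56, counting weight and AMH.

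**Validity.** In 5,000 simulated trials (r0 = ρ = 0.3, r10 = 0.7, no true effect; weight and AMH left out) the type I error was 4.7% without the 10 h value and 5.3% with it. Both are within about one Monte Carlo standard error (0.3 points) of 5%. With a true effect of 50 IU/L both models were unbiased. Power rose from 74% to 93% (r10 = 0.7) and from 73% to 81% (r10 = 0.5).

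**Comparisons null by design.** Four hormones at 4 h and 10 h give 8 of the 16 listed comparisons, if the 10 h sample is pre-dose. If each were tested at 5% and they were independent, the chance of at least one false positive would be 1 − 0.95⁸ = 34%. The values within a woman are correlated, so this is only indicative.

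**Timing.** With the SAP's 10 h interval, a 10 h sample can be pre-dose. With the protocol's 8–12 h, it could fall 10 − 8 = 2 h after the second injection and would then not be a baseline.

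**The case against.** The SAP model is valid: the first-dose response is shared, so it cancels between randomised arms in expectation, and change from pretrigger fairly compares a one-dose with a two-dose regimen. That stands. A reader might infer that the first-dose response distorts the contrast; it only adds noise.

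The gain is assumed, not documented. A reader might infer that the 10 h value is the strongest predictor available, or that pretrigger LH carries almost no information because of antagonist suppression. The documents support neither. They give no correlations. The undetectable LH mentioned in the SAP is a conditional finding on stimulation day 7, not the pretrigger value, and the last antagonist dose is 24 h before the trigger. Weight and AMH are already in the model and may absorb part of the gain. The protocol also describes a limited releasable pool of GnRH, so a strong first response could leave less for the second. The slope on the 10 h value might then differ between arms, and a common-slope covariate would gain less.

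A reader might also compute √(1 − r²) for r = 0.5 to 0.7 and quote a 13% to 29% cut. That compares with no adjustment at all, whereas the SAP already adjusts for the pretrigger value.

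The sample itself is not assured in all women, and its order relative to the injection is unstated. This puts conditions on the remedy but does not defeat it, because the SAP already commits to analysing a 10 h value.

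**Conclusion.** The point holds as a loss of precision in a secondary outcome. There is no bias, and the primary outcome is untouched. Relative to the SAP's own pretrigger adjustment, the pre-second-injection value would cut the standard error by about 11% to 26% (about 1.25 to 1.8 times the patients), assuming correlations of 0.3 for pretrigger, 0.5 to 0.7 for 10 h, and 0.3 between the two. If the 10 h correlation is only 0.2 to 0.3 and the pretrigger correlation is 0.5, the gain is nil and the cost is about one degree of freedom. The percentages assume a common slope and no contribution from weight or AMH. The LH-scale figures also rest on an SD from different women at a different dose.

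The varying interval might suggest counting sample times from the second injection instead. That would only move the blur: with 8–12 h between injections, 4 h after the second is 12 to 16 h after the first.

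**What to change.** In the SAP's hormone section:

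1. For the 14 h and 20 h comparisons, add the same hormone's value from the sample drawn before the second injection (nominal 10 h) as a covariate, keeping the pretrigger value, weight and AMH.
2. State that this sample is taken before the second injection, active or saline, in both arms.
3. Present the 4 h and 10 h values as descriptive pre-treatment data, not as between-arm effects.
4. Reconcile the sampling times in the SAP's study description (before, 12 h, 36 h, retrieval) with those under Secondary outcomes (4, 10, 14, 20 h), and the protocol's 8–12 h interval with the SAP's 10 h, so that the covariate exists and is pre-dose.
5. Name a method for a missing 10 h value.

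The cost is a few lines of SAP text and one degree of freedom per model. The main downside is that some women, such as those on less intensive sampling, may lack the 10 h value. The covariate should be specified before allocation is linked to the hormone data, since adding it later would look data-driven.

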Baseline covariates which may need adjusting for include age, number of embryos transferred, number of high quality embryos transferred, cause of infertility and BMI.

-Rates of OHSS :

[figure not shown]
Covariates which may need to be adjusted for would include number of follicles >11mm on final ultrasound scan prior to trigger, serum AMH or antral follicle count, number of eggs collected, pretrigger oestradiol level.

List trial data as per CONSORT guidance:

Number of women screened, number who withdrew, number not eligible, number of women recruited and meeting inclusion criteria, but excluded prior to randomisation for complications requiring other IVF treatments prior to receiving kisspeptin eg hydrosalpinx.

We expect to recruit 62 women eligible for randomization (31 per group).

Example:

Tables to be generated following study completion:

Table 1:

Sort by column A	SINGLE	DOIUBLE	BOTH
N	31	31	62
Age (y) C			
Weight (kg) I			
Body mass index (kg/m²) J			
Antral Follicle Count (AFC) F			
Serum AMH* (pmol/L) E			
% with average cycle length \geq35 days D\geq35			
Cause of infertility: G			
PCOS [‡]			
Tubal defect**			
Male Factor [†]			
Mixed			
Idiopathic (unexplained)			
Number of follicles[¶] BF			
Number of Follicles \geq 11mm[¶]			
BK			
Number of Follicles \geq 14mm[¶]			
BN			

Table 1: Baseline characteristics of patients who received kisspeptin-54 trigger. Contains medians (lower quartile, upper quartile) for continuous variables and totals (percentages) for categorical variables.

* AMH = anti-Müllerian hormone

‡ Anovulation due to Polycystic Ovarian Syndrome.

** Blocked or removed Fallopian tubes.

† Infertility is due to a problem with male partner's fertility.

¶ On final ultrasound scan during controlled ovarian stimulation prior to kisspeptin-54 trigger administration.

Table 2:

	SINGLE (n = 31)	DOUBLE (n = 31)	BOTH (n = 62)
Number of Oocytes BZ			
Number of Mature (M2) Oocytes CA			
Oocyte Maturation Rate (%) * CD			
Oocyte Yield (%) † CG			
Proportion achieving ≥60% oocyte yield (%) CH			
Number of 2 pronuclei (2PN) zygotes CE			
Proportion with at Least 4 eggs collected (%) CB			
Fertilization rate (%) ‡ CF			
Number of patients with embryo transfer CN≥1			
Number of Cleaved embryos at day 3 post ICSI CI			
Number of Embryos at day 3 graded as ≥623 CJ			
Number of Patients with day 5 transfer % with CM=5			
Number of Embryos at day 5 CK			
Number of High quality blastocysts (≥3A/B) CL			

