Number of High quality blastocysts (>3A/B) transferred CO			
Number of Embryos suitable for freezing CV			
Biochemical Pregnancy rate per protocol (%) CP including those who did not have transfer as 0			
Biochemical Pregnancy rate per transfer (%) CP not including those who did not have transfer			
Clinical Pregnancy rate per protocol (%) CQ			

including those who did not have transfer as 0

Clinical Pregnancy rate per transfer (%) CQ
not including those who did not have transfer

Implantation rate (%) Ψ CU

Live Birth rate per protocol (%)

Table 2: IVF outcome measures following kisspeptin-54 trigger. Contains means (standard deviation) for continuous variables and totals (percentages of N) for categorical variables

* Oocyte Maturation Rate is the percentage of oocytes collected which were mature.

† Oocyte Yield is the percentage of mature oocytes collected from the number of follicles

≥ 14 mm in diameter on the final ultrasound scan prior to kisspeptin-54 trigger administration.

‡ Fertilization rate is the percentage of mature oocytes which fertilize following intracytoplasmic injection with sperm (ICSI).

Ψ Implantation rate is defined as the percentage of embryos transferred which implant on assessment by ultrasound at 6 weeks of gestation.

Table 3:

Kisspeptin-54 Dose	SINGLE		DOUBLE	BOTH	
	N	31	31		
At least 1 oocyte retrieved BZ\geq1					
At least 1 mature oocyte retrieved CA\geq1					
At least 1 2PN zygote formed \ddagger CE\geq1					
Segmentation Ψ					
Number of patients with embryo transfer CN\geq1					
Number of patients with day 5 transfer* % with CM=5					
High quality embryo transfer\dagger CO\geq1					
Biochemical pregnancy at 11 days CP					
Clinical pregnancy at 6 weeks CQ					
Miscarriage / Still Birth (PENDING)					
Live Birth (PENDING)					

Table 3: Summary of patient response following kisspeptin-54 triggering.

The number of patients completing each criterion is shown (% in brackets).

\ddagger 2PN is two pronuclear zygote assessed on day following oocyte retrieval

Ψ Segmentation refers to cryopreservation of all embryos and embryo transfer in a subsequent frozen cycle due to high risk of OHSS

* Embryo transfer on day 5

\dagger Transfer of at least one high quality embryo. High quality embryos were blastocyst embryos graded on day 5 as being at least 3A or B in quality (Gardner et al. 2000).

Table 4:

	Early OHSS By single vs double	Late OHSS By single by double
OHSS Symptomatology		

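### Three covariates that the SAP lists for OHSS, pregnancy and implantation arise after the randomised second injection, and adjusting for them could remove part of its effect

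*SAP*

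**What the plan says.** The SAP's opening study description sets the order of events. All women receive a first kisspeptin injection. They are then randomised to a second kisspeptin dose or a "saline placebo injection at 10hrs following the first kisspeptin trigger injection". Retrieval is 36 h after the trigger, and one or two embryos are transferred 3-5 days after retrieval.

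Under Secondary outcomes, the text for pregnancy and implantation reads: "Baseline covariates which may need adjusting for include age, number of embryos transferred, number of high quality embryos transferred, cause of infertility and BMI". The list of possible covariates for OHSS includes follicle number before the trigger, then "serum AMH or antral follicle count, number of eggs collected, pretrigger oestradiol level". The word baseline is attached only to the first list. Both lists are worded permissively.

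The table shells classify some of the same variables differently:

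- "Table 1: Baseline characteristics of patients who received kisspeptin-54 trigger" has no row for eggs collected, embryos transferred or high quality embryos transferred.
- "Table 2: IVF outcome measures following kisspeptin-54 trigger" includes "Number of Oocytes BZ" and "Number of High quality blastocysts (>3A/B) transferred CO".
- The total number of embryos transferred has no row of its own in Table 2. It appears only through the number of patients with at least one embryo transferred.

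The SAP's secondary outcomes also include "embryo formation and quality, biochemical pregnancy rate", so embryo quality is an outcome in its own right.

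**The concern.** A randomised comparison of one against two doses estimates the total effect of the second dose when it is unadjusted, or adjusted only for variables fixed before randomisation. Eggs collected and embryos transferred are not fixed by then. They may be steps on the path from the second dose to OHSS or pregnancy. Holding them constant removes whatever part of the effect passes through them. If some unmeasured factor influences both the count and the outcome, adjustment can also introduce a further bias between arms.

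The effect at stake is a secondary one but clinically relevant: an OHSS excess with two doses, or a pregnancy gain, could be understated. An effect on egg number is not far-fetched in this trial, because the primary outcome is built from the mature oocytes collected.

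**Working it through.** **1. Order of events.** SAP times: retrieval at 36 h minus second injection at 10 h = 26 h after the randomised injection. Least favourable protocol times (section 6.1, doses up to 12 h apart; Appendix 2, retrieval from 32 h): 32 − 12 = 20 h. Transfer follows 3-5 days later. All three counts are post-randomisation under either document.

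**2. Covariates against the SAP's own tables.**

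| Covariate | Listed for | Table 1 (baseline) | Table 2 (outcomes) |
|---|---|---|---|
| Eggs collected | OHSS | no | yes, directly |
| High quality embryos transferred | pregnancy, implantation | no | yes, as high quality blastocysts transferred |
| Embryos transferred | pregnancy, implantation | no | only as patients with at least one |

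The other covariates in the two lists (age, cause of infertility, BMI, follicle number, AMH or antral follicle count, pre-trigger oestradiol) precede the trigger and raise no problem. So do those listed for the primary and hormone outcomes.

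**3. OHSS, illustration.** The plan has no figure to reproduce, and the documents give neither OHSS rates by arm nor an effect of the second dose on egg number. Every input here is an assumption. The 10% single-dose rate borrows the order of magnitude in Protocol 1.1 for moderate or severe OHSS, which refers to IVF cycles generally and not to kisspeptin.

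Model: X (baseline follicle score), U (unmeasured) and e are independent N(0,1); T is allocated 1:1.

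- Eggs = 12 + 3X + 2U + 3e + d·T
- logit P(OHSS) = b0 + 0.15·(eggs − 12) + c·U + g·T, with b0 set to give 10% under a single dose

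The true difference is the mean risk with T = 1 minus that with T = 0. The adjusted difference comes from logistic regression on T, X and eggs, standardised over all women (1,000,000 simulated). With g = 0.3 and c = 0:

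| Eggs added by second dose (d) | True excess, points | After adjusting for eggs |
|---|---|---|
| 0 | 2.9 | 2.8 |
| 0.5 | 3.7 | 2.9 |
| 1 | 4.5 | 3.0 |
| 2 | 6.4 | 3.2 |

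At d = 0 nothing material is lost. Over g = 0.3 or 0.6 and c = 0 or 0.5, the share lost is 11-31% at 0.5 egg, 20-51% at 1 egg and 33-76% at 2 eggs. Adjusting for X alone recovered the true difference within 0.1 point.

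**4. Pregnancy, exact arithmetic on assumed inputs, no direct effect of dose.**

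- High quality embryos: two transferred, risk 0.15 + 0.15 per high quality embryo, probability of high quality 0.35 against 0.45. Total effect = 2 × 0.15 × (0.45 − 0.35) = 0.030, or 3.0 points. At a fixed count the difference is 0.
- Number transferred: risk 20% with one and 35% with two, share receiving two 50% against 60% or 70%. Total effect = 0.15 × 0.10 = 1.5 points, or 0.15 × 0.20 = 3.0 points. At a fixed number the difference is 0.

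**5. Precision with 31 per arm (SAP).** Unadjusted 95% CI half-width = 1.96·√[(p1(1−p1) + p2(1−p2))/31].

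- 10% in both arms: 1.96·√(0.18/31) = 14.9 points
- 10% against 14.5%: 16.3 points
- 30% in both arms: 1.96·√(0.42/31) = 22.8 points

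The shifts in steps 3 and 4 lie well inside these intervals.

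**The case against.** The case for leaving the text alone has real substance.

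- **The wording is permissive.** The SAP commits to no model for these outcomes, whereas for hormones it names variables to be included. A reader might infer that the planned analysis will be biased. The documents do not support that: adjustment is only contemplated, and the effect of the second dose on the counts is unknown. What stands is that the lists allow such a model, and that the SAP does not say whether the adjusted or unadjusted comparison is the main one.
- **Implantation is different.** It is defined per embryo transferred, so it is conditional on transfer from the outset. A reader might extend the same criticism to it, but it has no total effect among all randomised women for adjustment to remove.
- **Table 2 does not list everything.** It would be too much to say that the SAP treats all three counts as outcomes; the total transferred has no row. For that variable the argument rests on timing alone.
- **Part of the remedy exists.** Table 2 already reports pregnancy with women without transfer counted as 0, separately from per-transfer rates, and Table 4 gives crude OHSS by arm. Missing are absolute differences with CIs, which the SAP states only under the primary outcome.
- **Some content is not visible.** A figure under the OHSS heading is not shown. The visible text states no aim of estimating a direct effect, but nothing can be said about the figure.
- **Intention to treat.** The protocol (sections 8.1 and 9) states it. That settles who is analysed, not which covariates are used, so it does not answer the point.
- **Importance.** The protocol's OHSS rationale is for replacing hCG, which both arms do. It does not make one against two doses on OHSS a central comparison.

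**Conclusion.** The point holds for OHSS and pregnancy as a risk of bias. The timing is certain from both documents: all three counts follow the randomised injection, and the two transfer counts are wrongly called baseline. Whether adjustment would distort the result depends on whether the second dose changes the counts. If it does, part of the total effect could be removed; if it does not, there is little bias.

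The size cannot be derived from the documents. The illustrations rest wholly on assumed rates, egg shifts and associations, and the percentage losses should be read beside the absolute shifts, which are a few points against half-widths of about 15 to 23. A reader might infer that a conclusion would be reversed; at 31 per arm that is unlikely from this cause alone. The problem is a possible systematic error in what is estimated, confined to secondary outcomes. It should be fixed because the correction is simple. The primary and hormone analyses are unaffected.

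**What to change.** 1. Delete number of eggs collected from the main OHSS model and both transfer counts from the main pregnancy model, and take the transfer counts out of the list headed as baseline.
2. Adjust these models only for a few of the pre-trigger covariates already listed, chosen in advance, since there are 62 women.
3. Report the unadjusted absolute difference with CI for OHSS and for pregnancy among all randomised women. For pregnancy, use the existing Table 2 rule that counts no transfer as 0.
4. Present implantation as a descriptive outcome conditional on transfer, and label any model containing egg or embryo counts as exploratory.

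The cost is SAP wording, with no new data and no change to the collected variables or table shells. The main models lose some explanatory adjustment, which remains available in the exploratory models.
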